Weaning From Mechanical Ventilation in Neurological Patients

NCT03128086

Date: March 3, 2017

INTRODUCTION

A high percentage of patients with acute neurological disease require invasive mechanical ventilation (MV) to isolate the airway, to provide adequate oxygenation and to prevent aspiration of gastric content (1-3). During weaning from MV, a spontaneous breathing trial (SBT) is realized before extubation in order to assess patient's capacity to breath (4-6), and reducing the risk of extubation failure. The extubation failure is associated with a prolonged length of stay in the intensive care unit (ICU) and in the hospital, as well as, more risk of infections and higher mortality (7). In neurological patients, a successful SBT can not predict exactly the success of extubation (8-10). It is necessary both the assessment of muscle strength and the ability to keep the airway clearance capacity to ensure success of extubation (8-15).

The results obtained with the application of weaning protocols in neurological patients are not conclusive (16), with the exception of one clinical trial (17). A meta-analysis concluded that the establishment of weaning protocols in subjects in a medical-surgical unit reduced the duration of MV by 25%, weaning time by 78% and ICU stay by 10%. These results support the use of weaning protocols in patients undergoing MV (18).

In this study we try to demonstrate that the use of a protocol-directed weaning in neurological patients will reduce the rate of extubation failure and associated complications. The primary objective is to reduce the failure rate of extubation. As secondary objectives we are going to analyse the incidence of infections, need for tracheostomy, duration of MV, length of ICU and hospital stay, and mortality at ICU, hospital and 90 days.

MATERIAL AND METHODS

A prospective interventionist no randomized study will be conducted in a medical-surgical ICU. Patients 18 years or older with acute medical or surgical neurological disease [acute ischaemic or haemorrhagic stroke, acute subarachnoid haemorrhage, traumatic brain trauma, metabolic encephalopathy (toxic, infectious as encephalitis or meningitis), scheduled neurosurgical surgery with a prolonged MV, and status epileptics], will be included. Exclusion Criteria: scheduled neurosurgical surgery (duration of MV <24 hours), neuromuscular disease,

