Conventional weaning (control group). Subjects in the control group will receive weaning from MV according to the usual procedure, by reducing level of PSV. Then a SBT will be performed through a T-tube (the same parameters as protocol study will be collected) and subsequent extubation of the patient if there is a successful SBT. The criteria for SBT and for extubation failure are the same than in the study group. In case of extubation failure, non-invasive ventilation will be not considered, but it left to the discretion of the attending physician.

STATISTIC ANALYSIS. Based upon previous results (10), the authors considered that the need for an intubation could be reduced by 13% (6) [26% in the control group vs. 13% in the study group]. The estimated sample size was 109 patients in each group (confidence interval $[1-\alpha] = 95\%$ ($P=0.05$) and power $[1-\beta] = 80\%$). A comparative analysis was conducted by using the Student's t-test or the Mann-Whitney test for a comparison of the quantitative variables for the parametric and non-parametric characteristics, respectively. For the qualitative variables, we used the Chi-Square statistic or Fisher's exact test. A statistical significance was reached if $P < 0.05$. The cumulative probability of survival was compared by using a Kaplan-Meier estimation of survival and a Log-Rank Test to compare both of the groups. Intention-to-treat

analysis will be realized. The data will be analysed with the aid of the statistical package SPSS 22.0.

REFERENCE

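### 109 patients per group gives about 68% power, not 80%, for 26% versus 13% under a two-sided 5% chi-square test

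*Combined protocol and SAP*

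**What the plan says.** The INTRODUCTION sets the endpoint that is sized: "The primary objective is to reduce the failure rate of extubation". This is a yes/no outcome for each patient.

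The STATISTIC ANALYSIS section gives the whole justification for the size of the trial. The assumed rates are "26% in the control group vs. 13% in the study group", an absolute reduction of 13 points said to rest on earlier results. The confidence level is 95% (P = 0.05) and the power 80%. The result is: "The estimated sample size was 109 patients in each group".

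On the analysis, the same section says: "For the qualitative variables, we used the Chi-Square statistic or Fisher's exact test". Significance is declared at P below 0.05. The section does not say whether the test is one- or two-sided, which sample-size formula was used, or whether 109 allows for patients without a primary outcome.

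**The concern.** All the inputs to a two-proportion sample size are in one paragraph, so the figure can be checked directly. 109 per group looks low for halving a 26% rate at two-sided 5% with 80% power.

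This paragraph is the only support for the trial's size, and it concerns the primary objective. If the true power is well below 80%, a non-significant result says less against the weaning protocol than a reader who trusts the plan would suppose. The plan does not call for a confidence interval on the effect, which would show that uncertainty.

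**Working it through.** **Inputs (STATISTIC ANALYSIS section).** p1 = 0.26 (control), p2 = 0.13 (study), difference d = 0.13, mean rate 0.195, equal groups, α = 0.05, power 80%. Two-sided testing is inferred from the named tests and the P < 0.05 rule; the plan does not state it. Normal quantiles: 1.960 (two-sided 5%), 1.645 (one-sided 5%), 0.8416 (80% power).

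**Standard-deviation terms.**
- Under no difference: a = √(2 × 0.195 × 0.805) = 0.5603.
- Under the planned difference: b = √(0.26 × 0.74 + 0.13 × 0.87) = √0.3055 = 0.5527.

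**Step 1. Try to reproduce 109, two-sided.** Pooled formula: n = (z_α·a + z_β·b)² / d²

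n = (1.960 × 0.5603 + 0.8416 × 0.5527)² / 0.13² = (1.0982 + 0.4652)² / 0.0169 = 144.6, so 145.

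Unpooled formula: n = (1.960 + 0.8416)² × 0.3055 / 0.0169 = 141.9, so 142.

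**Step 2. Try other formulas and the one-sided level.**

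| Method, 80% power | Two-sided 5%, n per group | One-sided 5%, n per group |
|---|---|---|
| Pooled | 144.6 (145) | 113.8 (114) |
| Unpooled | 141.9 (142) | 111.8 (112) |
| Arcsine | 142.1 (about 142) | 111.9 (112) |
| Continuity-corrected | 159.6 (160) | 129 |

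None gives 109. The nearest are the one-sided unpooled and arcsine figures of 112. An allowance for dropout raises n, so it cannot explain a figure that is too low.

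**Step 3. Power at 109 per group, two-sided.** Pooled formula: power = Φ[(d√n − z_α·a) / b]

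d√n = 0.13 × √109 = 1.3572; (1.3572 − 1.0982) / 0.5527 = 0.469; Φ(0.469) = 0.680.

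| Method at 109 per group | Power, two-sided 5% |
|---|---|
| Pooled normal formula | 68.0% |
| Unpooled normal formula | 69.0% |
| Exact enumeration, uncorrected chi-square | 69.0% |
| Exact enumeration, Fisher's test | 62.6% |

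One-sided 5% at 109 gives 78.5% (pooled) to 79.2% (exact chi-square).

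**Step 4. What effect does 109 detect with 80% power?** Holding the control rate at 26% and solving the pooled formula for the study rate gives 11.3%, a reduction of 14.7 points instead of 13.

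**Step 5. Could rounding of the rates explain it?** Take the rounding most favourable to the plan, 26.5% versus 12.5%. Two-sided n is then 124.5 (pooled) or 121.8 (unpooled), and power at 109 is 74.5%. The shortfall remains.

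**Step 6. Patients without a primary outcome (assumption).** The plan gives no figure. If 109 is the number included and a share of patients contribute no extubation result, the pooled two-sided power is:

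| Assumed share without outcome | n per group | Power |
|---|---|---|
| 5% | 104 | 66.0% |
| 10% | 98 | 63.4% |
| 15% | 93 | 61.1% |
| 20% | 87 | 58.2% |

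**The case against.** The best defence is that the calculation was one-sided. The objective is directional, the plan never states sidedness, and only a one-sided 5% level comes near 109. On that reading the power is 78.5% to 79.2%, close to what is claimed. The rates are also given as whole percentages. If they were rounded from 25.5–26.5% and 12.5–13.5%, the one-sided pooled formula runs from 98 to 134 per group, a range that contains 109. This much stands: an unstated one-sided calculation is the likely source, and with unrounded rates it could give exactly 109. It does not support 80% power for the analysis described. The plan states no one-sided hypothesis, and chi-square and Fisher tests at P < 0.05 are two-sided by default. Rounding does not rescue that reading (Step 5).

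A second objection is that the attrition point is weaker. The plan does not say whether 109 counts patients enrolled or analysed, and MATERIAL AND METHODS already excludes direct extubation, self-extubation, death without a weaning trial, and transfer. That is fair. Still, a study-group patient who does not meet the airway-clearance score may never be extubated, and tracheostomy is a listed outcome, so some loss is possible. Its size is unknown, and the main finding does not depend on it.

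A third is that the study is not randomised, so bias between groups may limit inference more than power does. That is true, but it does not make the stated 80% correct.

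**Conclusion.** The concern holds. For 26% versus 13% with a two-sided 5% test, 109 per group gives 68% to 69% power with chi-square and about 63% with Fisher's test. The stated 80% needs 142 to 145 per group (160 with continuity correction), so by the pooled formula the plan is 145 − 109 = 36 patients per group short. The chance of missing the planned effect is about 32%, not 20%, and about 37% if Fisher's test is used.

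This rests on the plan's own rates taken at face value, equal groups, a primary outcome for every patient, and the two-sided reading. If the sponsor did intend a one-sided 5% test, 109 would be only slightly short, but the plan would have to say so and analyse the data that way.

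**What to change.** Check the original calculation for its formula, sidedness and unrounded rates. Then replace the sample-size statement with wording such as:

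> With 109 patients per group, a two-sided 5% chi-square test has about 68% power to detect 26% versus 13%; 80% power is reached for 26% versus about 11%.

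Also:
- State that the primary test is two-sided and whether it is chi-square or Fisher's. If Fisher's, give about 63% in place of 68%.
- Say whether 109 counts patients included or patients with an extubation outcome.
- Report the primary result as a risk difference with a 95% confidence interval, so that a non-significant result is not read as no effect.

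The cost is a few sentences and a less favourable power figure. No extra patients are required. If the sponsor prefers to keep 80% power for 26% versus 13%, the alternative is 145 per group by the pooled formula, which is 72 more patients in total (290 instead of 218).

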spinal cord injury, tracheostomized, inability to be evaluated, severe multiple traumatic injuries evaluated by the Injury Severity Score (19), direct extubation and self-extubation, patients who died during their ICU stay (without a trial of weaning), and patients transferred to another hospital.

At ICU admission, the following variables will be collected: age, sex, body mass index, comorbidities, prognosis severity scale by Simplified Acute Physiological Score (SAPS) 3, Organ failure by Sequential Organ Failure Assessment (SOFA) (at ICU admission and 5 days after admission), reason for MV, the level of consciousness by Glasgow Coma Scale (GCS) at the time of intubation and where it was performed. During the ICU stay, all neurological treatments and procedures such as treatment of intracranial hypertension (mannitol or hypertonic saline, hyperventilation, decompressed craniotomy), cranial tomography (CT) scanner, external ventricular drainage, intracranial pressure sensor, cerebral arteriography, will be collected. The infectious complications (ventilator-associated pneumonia, tracheobronchitis, urinary tract infection, bacteraemia,) will be registered during the ICU stay.

To be included into study, subject undergoing mechanical ventilation will meet the following conditions: no or minimal sedation (propofol \leq 1mg/kg/h o midazolam \leq 0,1mg/kg/h), with spontaneous ventilatory stimulus, absence of intracranial hypertension, Glasgow Coma Score (GCS) $>$ 9 (motor $>$ 4 points), noradrenaline \leq 0,2mcgr/kg/min, (fraction of inspired oxygen)FiO₂ \leq 0.5 (positive end-expiratory pressure) PEEP of 5cmH₂O, no intervention scheduled in the next 48 hours, maximal inspiratory pressure (MIP) $<$ -20cmH₂O (20), occlusion pressure (P_{0.1}) $>$ 6mmHg with support pressure of 7cmH₂O and 0 cmH₂O of positive end-expiratory pressure (Z-PEEP).

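### Duration of ventilation and ICU and hospital stay are compared by t-test or Mann-Whitney with no rule for deaths, so these comparisons can mix mortality with speed of recovery.

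*Combined protocol and SAP*

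**What the plan says.** The Introduction lists among the secondary objectives "duration of MV, length of ICU and hospital stay, and mortality at ICU, hospital and 90 days". So the three durations and mortality are all outcomes of the same study.

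STATISTIC ANALYSIS gives one method for all quantitative variables: the groups are compared "by using the Student's t-test or the Mann-Whitney test for a comparison of the quantitative variables". Time-to-event methods appear only for death: "The cumulative probability of survival was compared by using a Kaplan-Meier estimation of survival and a Log-Rank Test". The analysis is declared to be "Intention-to-treat", and no survivors-only set is named for the durations.

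The exclusion criteria in MATERIAL AND METHODS remove "patients who died during their ICU stay (without a trial of weaning), and patients transferred to another hospital". Deaths in ICU after a weaning trial, and deaths later in hospital, are not removed.

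No section says how a patient who dies on the ventilator, in ICU or on the ward enters the duration comparisons. There are no ventilator-free days, worst-rank score, competing-risk analysis or survivors-only rule.

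**The concern.** A t-test or Mann-Whitney test on length of stay sees only a number of days. If all analysed patients are included, death on day 6 and discharge alive on day 6 get the same value. A group with more early deaths can then appear to recover faster.

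Unequal mortality is plausible here for two reasons. The Introduction says that extubation failure goes with higher mortality, and the plan hopes to halve the need for intubation ("26% in the control group vs. 13% in the study group"). Allocation is also uncontrolled ("A prospective interventionist no randomized study will be conducted in a medical-surgical ICU"), so case mix alone could separate the groups on mortality. A real benefit on stay could be hidden, or an apparent benefit could come from deaths.

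**Working it through.** **Plan's own figure.** The plan gives no figure for the durations or for mortality. Its one calculation, 109 per group, is for the primary endpoint. A one-sided 5% two-proportion formula comes near it: (1.645 + 0.842)² × (0.26×0.74 + 0.13×0.87) / 0.13² = 111.8. That is a separate matter; 109 is used below only as the group size.

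**Inputs.** From the documents: 109 per group, significance at P < 0.05, Mann-Whitney as one of the two named tests. Assumed, because the documents give no death rates, times or SDs: ICU mortality 25% in one group and 12% in the other; log-normal ICU stay with log-SD 0.6; survivors' median 14 days in both groups, so no true difference in survivors' stay; median time to death m varied over 6, 10, 14 and 20 days.

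**Mean stay.** A log-normal mean is the median × exp(0.6²/2) = median × 1.197. The higher-mortality group is shorter on average by (0.25 − 0.12) × (14 − m) × 1.197 days.

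**Mann-Whitney.** Let q be the probability that a death time is shorter than a survivor's stay: q = Φ(ln(14/m) / (0.6√2)). The probability that a patient in the higher-mortality group has the shorter stay is θ = 0.5 + 0.13 × (q − 0.5). The standard error with no difference is √((2×109 + 1) / (12×109²)) = 0.0392. The chance that the higher-mortality group is declared significantly shorter is about Φ((θ − 0.5)/0.0392 − 1.96).

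| Median time to death | q | Mean gap (days shorter) | θ | Declared significantly shorter, formula | Simulation |
|---|---|---|---|---|---|
| 6 | 0.841 | 1.25 | 0.544 | 20% | about 20% |
| 10 | 0.654 | 0.62 | 0.520 | 7% | about 7% |
| 14 | 0.500 | 0 | 0.500 | 2.5% | about 3% |
| 20 | 0.337 | −0.93 | 0.479 | 0.6% | below 1% |

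In the last row the bias has reversed. The higher-mortality group looks about 0.9 days longer, significantly so in 8% to 9% of trials.

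**A second timing model.** Each death cuts short an underlying stay that has the same distribution in both groups. Deaths fall anywhere in that stay or only in its second half, and the log-SD runs from 0.5 to 1.0. The higher-mortality group is declared significantly shorter as follows:
- 20% vs 10% mortality: 4% to 12% by Mann-Whitney, 3% to 10% by t-test.
- 30% vs 10%: 6% to 34% and 5% to 26%.
- 10% vs 10%: about 2% to 3% by either test, so no bias.

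**A death-aware outcome.** In the 25% vs 12% case, ICU-free days to day 28 with death scored 0 favour the lower-mortality group by 1.6 days. A significant result for the higher-mortality group is almost never seen. The lower-mortality group is significantly better in about 31% of trials although survivors' stay is identical, so that difference comes from mortality alone.

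**Reach.** Only ICU stay was modelled on its own inputs. Hospital stay is open to the same mechanism through any in-hospital death. MV duration is cut short only by deaths while ventilated; a patient extubated alive who dies later has a complete value.

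**The case against.** The strongest objection is that the documents do not say that death counts as an ordinary end of stay. A reader might infer that rule from the choice of tests, but the text is silent, and a survivors-only comparison would fit it too. This stands as a limit on the wording. Counting death that way is the default result of the stated tests under intention-to-treat, not a rule the plan adopts. It does not remove the point: a survivors-only comparison would bring its own selection bias, so a rule is needed on either reading.

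A reader might also infer that a protocol lowering mortality must appear to lengthen stay. The documents do not support that, because nothing in them says that deaths come early. The entry conditions (minimal sedation, no intracranial hypertension, a minimum coma score, limited vasopressor and oxygen) and the exclusion of ICU deaths before a weaning trial probably remove many early deaths and lower the remaining mortality. The 6-day case is one possibility, and the sign turns on that input.

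Finally, free-days answer a different question from duration and can differ through mortality alone. That is correct, and it limits how they may be interpreted. Worst-rank or competing-risk analyses are also defensible.

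**Conclusion.** The point holds in conditional form. The plan names tests for the three durations and leaves deaths without a rule, while deaths after a weaning trial stay in the analysis. Followed as written, these comparisons mix mortality with speed of recovery whenever mortality differs and deaths and live discharges differ in timing.

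On the assumed inputs, the chance of a misleading result for ICU stay runs from about 20% with early deaths down to the nominal 2.5% when the timings coincide, and the bias reverses with late deaths. These figures illustrate the mechanism and do not predict this trial. The effect is less certain for MV duration, which depends on deaths while ventilated. The primary endpoint, extubation failure, is not touched. This is a worthwhile, low-cost improvement to secondary analyses, not a flaw in the main comparison.

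**What to change.** In STATISTIC ANALYSIS, state how deaths enter the three outcomes. One workable choice is ventilator-free and ICU-free days to day 28 and hospital-free days to day 90, counted from inclusion, with death within the window scored 0 and tested by the Mann-Whitney test already planned. A worst-rank score, or a competing-risk analysis of successful extubation and of discharge alive, would also serve. Report raw durations descriptively, separately for survivors and non-survivors.

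The cost is mainly wording. The dates required (extubation, ICU and hospital discharge, death) are implied by the stated outcomes, but the variable list in MATERIAL AND METHODS does not name them and should. The downside is one of interpretation: free-days combine death and duration, so they must stand beside the mortality results and not be read as a pure effect on duration.

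### The study is not randomised, yet every planned outcome comparison is unadjusted, so prognostic differences between the groups are reported as effect of the weaning protocol

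*Combined protocol and SAP*

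**What the plan says.** Material and Methods sets the design: "A prospective interventionist no randomized study will be conducted in a medical-surgical ICU". No section says how a patient is placed in one group or the other, or whether the groups run at the same time.

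The Introduction gives the target: "The primary objective is to reduce the failure rate of extubation". That outcome is binary, so the Statistic Analysis section covers it with one sentence: "For the qualitative variables, we used the Chi-Square statistic or Fisher's exact test". Quantitative outcomes get Student's t-test or Mann-Whitney, and survival gets Kaplan-Meier with a log-rank test. Intention-to-treat is stated. The section names no regression, propensity score, matching, stratification or sensitivity analysis for confounding.

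Prognostic data are nevertheless collected at ICU admission: "age, sex, body mass index, comorbidities, prognosis severity scale by Simplified Acute Physiological Score (SAPS) 3", together with SOFA, the reason for ventilation and GCS at intubation. A common set of entry conditions applies to both groups: "To be included into study, subject undergoing mechanical ventilation will meet the following conditions". The Introduction also says of extubation in these patients: "It is necessary both the assessment of muscle strength and the ability to keep the airway clearance capacity to ensure success of extubation".

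**The concern.** The stated aim is causal: to demonstrate that protocol-directed weaning lowers extubation failure. Without randomisation, a crude test compares two groups as they happened to be formed. If they differ in something that predicts failure, the crude difference mixes that with the protocol effect, and no planned analysis would separate the two.

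The case mix leaves room for this. It includes "acute ischaemic or haemorrhagic stroke, acute subarachnoid haemorrhage, traumatic brain trauma", as well as encephalopathy, neurosurgery and status epilepticus. The entry conditions place no upper limit on age, no limit on comorbidity and no balance on diagnosis. The admission variables may be tabulated by group, but that only displays an imbalance; it corrects nothing. Choosing an adjustment after seeing the table would invite selective reporting. The bias could create a benefit that is not there or hide one that is.

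**Working it through.** **1. Inputs from the plan (Statistic Analysis).** Failure 26% (control) versus 13% (study), 109 per group, significance at P < 0.05, power 80%.

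**2. The plan's own figure.** n = (z_α + z_β)² × [p₁(1−p₁) + p₂(1−p₂)] / (p₁−p₂)², with the bracket 0.1924 + 0.1131 = 0.3055 and (0.13)² = 0.0169.
- One-sided 5%: 6.183 × 0.3055 / 0.0169 = 111.8, so 112, within 3% of 109.
- Two-sided 5%: 7.849 × 0.3055 / 0.0169 = 141.9, so 142.

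So 109 is approached only one-sided. That is a separate sample-size matter; the present point does not depend on it.

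**3. Assumed inputs for the illustration.** One binary predictor of failure with 50% overall prevalence; odds ratio (OR) 2 or 4; prevalence differing between groups by 10 points (55% vs 45%) or 20 points (60% vs 40%). None of these comes from the documents.

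**4. No true effect.** Solve (r₀ + r₁)/2 = 0.26 with [r₁/(1−r₁)] / [r₀/(1−r₀)] = OR. This gives r₀, r₁ = 19.4%, 32.6% (OR 2) and 13.5%, 38.5% (OR 4). Group risk = prevalence × r₁ + (1 − prevalence) × r₀. For OR 4 and 20 points: 0.6 × 38.5 + 0.4 × 13.5 = 28.5% and 0.4 × 38.5 + 0.6 × 13.5 = 23.5%. The rejection rate is by exact enumeration of both binomials (n = 109 each), two-sided chi-square at 5% without continuity correction.

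| Scenario | Spurious difference (points) | False-positive rate |
|---|---|---|
| No imbalance | 0 | 5.2% |
| OR 2, 10 points | 1.3 | 5.7% |
| OR 4, 10 points | 2.5 | 7.2% |
| OR 2, 20 points | 2.6 | 7.5% |
| OR 4, 20 points | 5.0 | 13.7% |

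**5. True effect 26% versus 13%.** Study-group stratum risks at OR 4, averaging 13%, are 5.9% and 20.1%.

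| Scenario (OR 4, 20 points) | Control vs study | Chance of significance |
|---|---|---|
| No imbalance | 26% vs 13% | 69.0% |
| Study group higher-risk | 23.5% vs 14.4% | 40.6% |
| Control group higher-risk | 28.5% vs 11.6% | 89.1% |

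**6. Do the entry conditions remove the problem?** Suppose a normal factor differs by 0.5 SD before screening and both groups pass the same cut-off c. The mean above c is μ + φ(c−μ)/[1−Φ(c−μ)]. At c = 0 (the control mean) this is 0.798 and 1.009, leaving 0.21 SD. For c = −0.5 and +0.5 the remainder is 0.28 and 0.16 SD. Restriction shrinks the difference but does not remove it.

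**7. Does adjustment work at this sample size?** Expected failures: 109 × 0.26 + 109 × 0.13 = 28.3 + 14.2 = 42.5, or 4.3 per term with 10 terms and 2.8 with 15. That is too few for an unpenalised outcome model. Propensity-score overlap weighting was therefore simulated (40,000 runs per scenario; variance allowing for estimation of the weights):
- False-positive rate 5.0% to 5.4% in all the scenarios above, with 10 or 15 terms that include the predictor.
- Power at OR 4, 20 points: 66% to 69% in both directions, against 69% unadjusted with balanced groups.
- With the predictor left out of the weighting model (20,000 runs), the false-positive rate stays at 13.5%.

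**The case against.** The strongest reply is that no size for the bias comes from the documents. Prevalence, odds ratios and imbalance are all assumed, and in three of the four null scenarios the false-positive rate is at most 7.5%. That is correct. The case rests on the design, with no randomisation and no adjustment, and not on the illustration. The illustration does, however, concern a single factor.

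Second, common entry limits on consciousness, oxygenation, vasopressor dose and respiratory strength make the groups more alike. This stands as a mitigation, so the concern is with differences that remain after entry; step 6 shows that they can.

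Third, intention-to-treat is planned. It preserves a balance created by randomisation, and here there is none to preserve.

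Fourth, the Introduction's remark on muscle strength and airway clearance is about clinical assessment and does not by itself require an adjusted model. That is fair. It shows only that the authors regard patients as differing in ways that matter for extubation success.

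Finally, adjustment deals only with measured factors, and its value depends on how the groups are formed, which is unstated. That also stands. It is why the allocation rule comes first in the fix and why the conclusion must be worded with care.

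**Conclusion.** The concern holds and should be fixed before the analysis. Both facts are explicit: the study is not randomised, and only unadjusted comparisons are planned. Followed exactly, the plan would report any remaining prognostic difference between the groups as effect of the weaning protocol.

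Size and direction cannot be derived from the documents. The spurious differences of 1.3 to 5.0 points, set against a planned 13, hold only under the assumed predictor and imbalances. That the collected variables predict extubation failure is likewise an assumption, though a reasonable one for severity, consciousness and diagnosis.

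**What to change.** 1. **Allocation.** State how patients enter each group and whether the groups are concurrent. If they are sequential, say that baseline covariates cannot remove a time trend.
2. **Primary analysis.** Pre-specify one adjusted estimate: the risk difference in extubation failure with a 95% confidence interval, patients kept in their assigned group. Propensity-score overlap weighting with robust or bootstrap variance is suitable. Say that it targets patients who could plausibly have been in either group. Another single method fixed in advance, such as a penalised outcome model with standardisation, is acceptable.
3. **Covariates, all from before weaning.** Age, comorbidities (coding fixed in advance), SAPS 3, admission SOFA, GCS at intubation, and reason for ventilation: 10 terms if the last is coded as the six disease groups (rare ones merged). If reason for ventilation is recorded as something other than diagnosis, name diagnosis explicitly. Adding sex, body mass index and the entry values of GCS, MIP and P0.1 makes 15. State that the entry values are recorded in both groups; they must be measured anyway to apply the entry conditions. If they are unavailable, name them as unadjusted.
4. **Leave out** day-5 SOFA, treatments or measurements after weaning starts, and the airway-clearance score, which is part of the intervention.
5. **Other outcomes.** Apply the same adjustment to survival and the other secondary outcomes. Keep the planned unadjusted tests as supportive.
6. **Conclusion.** Report an adjusted association with possible residual confounding. This includes airway-clearance capacity: it is unclear whether the statement that controls have the same parameters collected extends to that score.

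**Cost.** About a paragraph of text, one sentence on allocation, one on recording entry values, and some analysis work. Another package is needed if SPSS 22.0 does not give robust variance for a weighted model.

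Precision falls. The simulated effective sample is 95% (10 terms) or 93% (15 terms) without imbalance, and 92% or 89% with a 20-point imbalance in one factor. If nine continuous covariates also differ by 0.2 or 0.3 SD, it is 82% or 74% with 15 terms, and power is 63% or 59%. Robust variance that treats the weights as fixed costs about 2 points more.

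If the sample size is revisited, the usual pooled-variance formula gives 145 per group (two-sided). This would become about 153 (145/0.95) to 182 (145/0.80) if the covariates explained an assumed 5% to 20% of the variation in group membership.
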